#### **5.5.4 Instructions for prescribing and taking study treatment**

Study drug will be single-blind during the placebo run-in and double-blind, placebo-controlled after randomization. At clinic visits, patients will receive a witnessed dose of study drug and, therefore, will be instructed to withhold study drug and SoC asthma therapy prior to each clinic visit. These in-clinic witnessed doses should be given after completion of all pre-dose assessments and at approximately the same time at each clinic visit. Between clinic visits, patients will take study drug once daily in the morning. Patients will be instructed to take their study drug at approximately the same time each morning, with or without food.

At Visit 101, all eligible patients will be given oral placebo to QAW039 during the placebo run-in period for approximately 1 week and will be instructed on the intake of study drug. **In order to maintain the blind from the patient's point of view, investigators must not divulge information regarding the fact that all individuals will be assigned to placebo during the placebo run-in period.** At Visit 201, patients will be randomized and stratified according to patient age (<18 or ≥18 years) and use or non-use of a second asthma controller medication at Visit 1. Treatment randomization will be stratified at the regional level. Each randomized patient will then enter a 12-week treatment period where they will receive one of the following 2 treatments: (1) QAW039 150 mg once daily given orally or (2) matching placebo to QAW039 150 mg once daily given orally. The study drug will be dispensed in kits at each site visit during the treatment period to cover the treatment period between patient visits and to allow for late visits and other unforeseen events. All dosages prescribed and dispensed to the patient during the study must be recorded on the dosage administration record (DAR) CRF. All kits of study drug assigned by IRT will be recorded/databased in the IRT system.

The investigator must promote compliance by instructing the patient to take the study drug exactly as prescribed and by stating that compliance is necessary for the patient's safety and the validity of the study. The patient must also be instructed to contact the investigator if he/she is unable for any reason to take the study drug as prescribed.

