#### 9.4.1 Primary Variable(s)

The primary variable for this study is the change from baseline in pre-dose FEV1 at the end of 12 weeks of treatment. Pre-dose FEV1 is the average of the two FEV1 assessments taken at 45 minutes and 15 minutes prior to the dosing of study drug at the clinic visit. The baseline FEV1 is defined as mean of the two FEV1 assessments prior to the first dose of study drug at the randomization visit. If any one of these assessments is missing (or is not confirmed to be pre-dose), then the remaining non-missing observation will be considered as baseline. If both assessments are missing (or are not confirmed to be pre-dose) then the last available FEV1 measurement prior to Day 1 on study drug will be used for baseline. If the FEV1 measurements are missing both on Day 1 and at the placebo run-in or screening visits, the respective baseline values will be set to missing.

The secondary variables are daytime asthma symptoms, total daily SABA use and AQLQ+12. Their definition and analysis is described in [Section 9.5](#).

Efficacy measurements (i.e., daily asthma symptom scores, FEV1) taken within 7 days of systemic corticosteroid use and/or within 6 hours of rescue medication (SABA) use will be censored (set to missing). Additionally, if the pre-dose FEV1 is taken within 12 hours of LABA (including fixed dose combinations of LABA and ICS) use or 24 hours of tiotropium, then the individual FEV1 value will be set to missing.

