#### 9.5.1.1 Daytime asthma symptoms in patients

Daytime asthma symptoms are evaluated through four questions and each of them will be rated on a scale of 0 to 6. Higher scores indicate more severe asthma-related symptoms. A mean score will be calculated for the responses to 4 questions. The main analysis of the secondary endpoint of daytime symptoms will be performed for all patients over the entire age range (12 years and older). The baseline of daytime asthma symptoms will be defined as the average of the mean daytime asthma symptom score during the placebo run-in period. The mean of change from baseline in the daytime symptom scores over the 12 weeks of treatment will be analyzed using an analysis of covariance (ANCOVA) model in a similar fashion as the primary efficacy variable. The null hypothesis is that the treatment difference compared to placebo over the 12 weeks of treatment = 0, while the alternative hypothesis is that the treatment difference to placebo over the 12 weeks of treatment  $\neq$  0. This model will be fitted to each of multiple imputations generated using a jump-to-reference approach as for the primary analysis.

The asthma diary included in this study to measure daytime asthma symptoms was validated in studies of patients aged 18 to 65 years ([Santanello et al 1997](#)). It was subsequently included as a measure in placebo-controlled studies of montelukast in patients aged 15 years and older ([Reiss et al. 1998](#) and [Malmstrom et al. 1999](#)) and shown to be responsive to both montelukast and inhaled beclomethasone therapy in this age range. Given the performance characteristics, particularly the responsiveness to asthma therapies, of the asthma diary are known for patients aged 15 years and older, a supportive analysis of the secondary endpoint of daytime symptoms will be included and be limited to patients aged 15 years and older.

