PEF	Peak Expiratory Flow
PK	Pharmacokinetics
PPS	Per protocol set
PR	Pulse Rate
PT	Preferred Term
Qd	Qua'que di'e / once a day
QTc	Corrected QT interval

QTcF	Fridericia QT correction formula
RAN	Randomized set
SABA	Short Acting Beta2 Agonist
SAE	Serious Adverse Event
SAF	Safety analysis set
SAP	Statistical Analysis Plan
SBP	Systolic Blood Pressure
SD	Standard Deviation
SI	International System of Units
SoC	Standard of Care
SOC	System Organ Class
TEAE	Treatment Emergent Adverse Event
TFL	Tables, Figures, Listings
WHO-DD	World Health Organization- Drug Dictionary

1 Introduction

This document contains details of the statistical methods that will be used in the phase III clinical trial CQAW039A2316. This study is designed to determine efficacy and safety of QAW039 (150 mg once daily), compared with placebo, when added to standard-of-care (SoC) asthma therapy in adult and adolescent (≥ 12 years) patients with uncontrolled asthma with respect to change from baseline in FEV₁ at the end of 12 weeks of treatment.

Data will be analyzed according to Section 9 of the study protocol.

Important information is given in the following sections and details are provided, as applicable, in Section 6: [Appendix](#).

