2.1.1.1 Baseline definition

Data from unplanned visits prior to screening are not included in analysis. In general, baseline is defined as the last assessment taken prior to the first dose of study drug at Day 1 (Visit 201).

Checks will be performed to ensure the assessments were taken prior to the first dose of study drug on Day 1 (Visit 201). If the assessment is missing or not confirmed to be pre-dose, then the last available non-missing assessment will be used as baseline. Missing baseline pre-dose FEV1, daytime asthma symptoms, total daily SABA use and AQLQ+12 will be assumed to be missing at random as assessments are performed prior to any knowledge of treatment allocation and will be imputed using the mean value of all randomized patients.

Table 2-1 Baseline definition of analysis parameters

Parameter	Baseline assessment	Detail
ACQ-5, AQLQ [REDACTED]	Last assessment prior to the first dose of study drug on Day 1	If the Day 1 assessment is missing the last available assessment (scheduled or unscheduled) taken prior to the first dose of study drug will be used.

Lung function (FEV ₁)	Average of the two FEV ₁ assessments taken at 45 minutes and 15 minutes prior to the first dose of study drug on Day 1	Checks will be performed to ensure both values were taken prior to the first dose of study drug. If one of the 45 and 15 min values is missing (or is not confirmed to be pre-dose) then the remaining non-missing value will be taken as the baseline. If both assessments are missing (or are not confirmed to be pre-dose) then the last available FEV ₁ measurement (scheduled or unscheduled) prior to Day 1 will be used for baseline.
eDiary data (Daytime asthma symptoms)	Average of the mean daytime asthma symptom score from Visit 101 to Day 1	The baseline score will be calculated as long as there are at least 4 days with non-missing eDiary data. Noted that the morning assessment for Day 1 counts towards the baseline.
eDiary data (Total daily use of SABA)	Average of total daily SABA use from Visit 101 to Day 1	The baseline score will be calculated as long as at least 4 days with non-missing eDiary data. Noted that the morning assessment for Day 1 counts towards the baseline while the evening assessment for Day 1 counts as the treatment period.

Laboratory data (hematology, clinical chemistry, urine analysis)	Last available assessment (scheduled or unscheduled) prior to dosing on Day 1	

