2.6 Analysis of secondary efficacy objective(s)

2.6.1 Daytime asthma symptoms in patients

Daytime asthma symptoms are evaluated through four questions and each of them will be rated on a scale of 0 to 6. Higher scores indicate more severe asthma-related symptoms. A mean score will be calculated for the responses to 4 questions. The main analysis of the secondary endpoint of daytime symptoms will be performed for all patients over the entire age range (12 years and older).

The mean of change from baseline in the daytime symptom scores over the 12 weeks of treatment will be analyzed based on on-study data (including on-treatment and off-treatment data) using an analysis of covariance (ANCOVA) model in a similar fashion as the primary efficacy variable.

The model will include factors for treatment group, age group (<18 vs. ≥ 18 years), use or non-use of a second asthma controller medication at study entry, and region, as well as the baseline

daytime asthma symptom score, baseline total daily SABA use and baseline pre-dose FEV₁ as continuous linear covariates.

The least squares mean (“adjusted mean”) change from baseline for each treatment group, the difference in the least squares mean changes between the two treatment groups (QAW039 150 mg – placebo), and the two-sided 95% confidence interval along with the superiority p-value for the difference will be obtained. This model will be fitted to each of multiple imputations generated using the approach described in [Section 2.6.4](#).

In addition, the mean of change from baseline in the daytime symptom scores by 4-week intervals over the 12 weeks of treatment will be analyzed based on on-treatment data using a MMRM model in which treatment, age group (<18 vs. ≥18 years), use or non-use of a second asthma controller medication at study entry, region, interval and treatment-by-interval interaction will be included as fixed-effect factors, and baseline pre-dose FEV₁ value as well as the baseline daytime asthma symptom score, baseline total daily SABA use and interval-by-baseline daytime asthma symptom score as covariates. A common unstructured covariance matrix among visits for each treatment group will be used. The analysis will be performed based on all available on-treatment data up to week 12. The estimated treatment differences for all treatment comparisons will be tabulated along with the associated 95% confidence intervals and their two-sided p-values.

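### The protocol censors daily symptom scores recorded near SABA or systemic corticosteroid use, the symptom-endpoint rules omit that step, and no readable SAP text withdraws it

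*Protocol*

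**What the plan says.** **Protocol 9.4.1** sets to missing efficacy measurements, "i.e., daily asthma symptom scores, FEV1) taken within 7 days of systemic corticosteroid use and/or within 6 hours of rescue medication (SABA) use". Just before that sentence it turns to the secondary variables and says: "Their definition and analysis is described in" Section 9.5.

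**Protocol 9.5.1.1** builds the daytime symptom endpoint from the mean of four items. On baseline it says "The baseline of daytime asthma symptoms will be defined as the average of the mean daytime asthma symptom score during the placebo run-in period". It has no censoring step.

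**SAP 2.1.1.1, Table 2-1** gives the baseline as "Average of the mean daytime asthma symptom score from Visit 101 to Day 1", with the condition that "The baseline score will be calculated as long as there are at least 4 days with non-missing eDiary data". Neither SABA nor corticosteroid use is mentioned.

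**SAP 2.6.1** says the mean change over 12 weeks "will be analyzed based on on-study data (including on-treatment and off-treatment data"). **SAP 2.6.4** forms weekly means from weeks with at least four usable days and imputes the remaining weeks. Neither section has a medication-based exclusion.

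**SAP 1** states: "Data will be analyzed according to Section 9 of the study protocol". **SAP 4** lists departures from the protocol, including small ones such as how age is derived. No readable item there withdraws the 9.4.1 rule.

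**The concern.** A rule that names the symptom score sits in the protocol section on the primary variable and is absent wherever the symptom endpoint is actually defined. The SAP imports protocol Section 9 as a whole, so a programmer could defend either dataset. The endpoint is H2 in the multiplicity scheme, and a confirmatory test should not have two defensible inputs at unblinding.

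Neither reading is clean. If the rule is applied, missingness is created by symptoms (through SABA use) or by exacerbations (through corticosteroid use). Intermittent missing weeks on treatment are then imputed under missing at random. If it is not applied, an explicit Section 9 rule has been dropped without being listed as a change.

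**Working it through.** **1. Significance level at stake.** SAP 2.5.6 splits 98% of alpha equally between symptoms and SABA use: 0.98 × 0.05 / 2 = 0.0245. Protocol Table 9-2 and SAP Table 3-2 print the same figure.

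**2. Does the stated power depend on the rule?** The tables give 74% at 0.0245 and 83% at 0.05, with a difference of 0.26, SD 0.94, 325 per arm and 15% discontinuation, half of whom complete. As a closed-form approximation, let all 15% lose the effect and 7.5% have no data:

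- difference = 0.26 × 0.85 = 0.221
- n per arm = 325 × 0.925 = 300.6
- power = Φ(0.221 / (0.94 × √(2/300.6)) − z) = 73.7% at 0.0245 and 82.2% at 0.05

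This agrees with the stated figures to within a point without any censoring step. The power statement therefore gives no sign that the rule was planned for, and it is not put in doubt here.

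**3. Can the SABA clause be carried out?** Protocol 6.4.2.2 has patients enter, morning and evening, the puffs taken over the preceding 12 hours. An entry of zero puffs is clearly uncensored. For an entry of one or more puffs, nothing described places the use inside or outside a 6-hour window. Any working version would be a choice made outside the plan.

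**4. Does the clause suit the score?** Six hours is the SABA washout before spirometry (Protocol Table 5-2), where the measurement is made at one moment. The daytime diary questions (Protocol 6.4.2.1) ask about the whole current day, and Protocol 5.5.6 has patients take SABA for symptoms. Removing scores near SABA use would tend to remove the more symptomatic days.

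**5. Day-count thresholds, SABA clause.**

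- Weekly mean (SAP 2.6.4, minimum four days): 7 − 4 = 3, so it is lost at four censored days.
- Baseline, if seven scores exist: 7 − 4 = 3, lost at four.
- Baseline, if every date from Day −7 (Visit 101 in Protocol Table 6-1) to Day 1 counts: there is no Day 0, so 7 + 1 = 8 dates. Then 8 − 4 = 4 is kept and 8 − 5 = 3 is lost.

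Inclusion criterion 7 requires SABA use on four of the last seven run-in days. At the extreme, if every such day were censored, a patient with the minimum four would keep at most three of seven scores. Protocol 5.5.4 describes patients being "given oral placebo to QAW039 during the placebo run-in period for approximately 1 week", so the number of available days varies. Loss of a patient's own baseline is possible but not certain. If it is lost, SAP 2.1.1.1 substitutes the mean of all randomized patients.

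**6. Day-count thresholds, corticosteroid clause.** Take a 3-day course, the shortest that Protocol 6.4.3 counts as an exacerbation, lying wholly within weeks 1 to 12 with all other days usable.

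- Window after use only: 3 + 7 = 10 days.
- Window in both directions: 7 + 3 + 7 = 17 days.

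Weekly means left with fewer than four days, by the weekday on which the window starts:

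| Window | Day 1 | 2 | 3 | 4 | 5 | 6 | 7 |
|---|---|---|---|---|---|---|---|
| 10 days | 1 | 2 | 2 | 2 | 1 | 1 | 1 |
| 17 days | 2 | 3 | 3 | 3 | 2 | 2 | 2 |

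For example, a 10-day window starting on day 2 takes six days of the first week and four of the next, so both are lost.

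**The case against.** The best defence is that the documents can be read together. The SAP adopts protocol Section 9, which includes 9.4.1. Censoring there means setting to missing, and the SAP diary rules operate on days that are not missing. Those rules could simply sit downstream of the protocol rule, and the pointer to Section 9.5 does not cancel the sentence that follows it. On that reading the rule applies and nothing was dropped. This stands as a possible reading, but it does not rescue the plan. It leads straight to the SABA clause, which cannot be worked out from the diary and does not fit a whole-day score.

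Three limits are fair:

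- One bullet in SAP Section 4 is blank, so the absence of a retraction holds for readable text only. The bullet sits among analyses moved outside the study report, an unlikely place to retract a data rule.
- That censoring would fall on more symptomatic days is an inference from how the score and the SABA instructions are worded; no data in the documents show it. SAP Table 2-2 gives a reason for excluding readings close to asthma medication, but only for FEV1.
- No effect on H2 is quantified. The frequency of censoring, any difference between arms and the rate of corticosteroid courses are not in the documents.

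It can also be said that SAP Table 2-2 has no systemic corticosteroid entry for FEV1 although 9.4.1 covers it. That is true and can be settled in the same edit.

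**Conclusion.** The concern holds. The mismatch is certain on the readable text. Beyond the mismatch, the SABA clause as written is the wrong rule for this score. Whether and in which direction the corticosteroid clause applies to diary scores is a point to clarify.

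The size can be given only as the day-count thresholds above, which assume no other diary gaps and, for corticosteroids, a 3-day course; longer courses remove more. The effect on the H2 estimate or its error rate cannot be computed. No effect on the primary FEV1 comparison is shown. Read on its own, the SAP points to uncensored scores, so the correction mostly confirms what it already implies. This should be fixed before unblinding.

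**What to change.** In SAP 2.1.1.1, 2.6.1 and 2.6.4, state that every recorded daytime symptom score is used regardless of SABA timing, at baseline and afterwards, and that the 6-hour SABA exclusion applies to FEV1 only. In the same edit, state whether the 7-day corticosteroid censoring applies to diary scores and, if so, whether the 7 days run after use only or in both directions. It would be sensible to state there too whether that clause still applies to FEV1. List the change from protocol 9.4.1 in SAP Section 4.

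The cost is a short clarification in three places and one Section 4 entry, completed before unblinding, with no new data. The protocol wording can be aligned at the next amendment, with the usual approvals.

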#### 9.4.2 Statistical model, hypothesis, and method of analysis

The primary objective of the study is to evaluate superiority of QAW039 150 mg once daily over placebo (with SoC asthma therapy as the background therapy) by testing the following null hypothesis ( $H_0$ ) versus the alternative hypothesis ( $H_a$ ):

[figure not shown]
$H_0$ : There is no difference in the change from baseline in pre-dose FEV1 at week 12 post-baseline for the patients treated with QAW039 150 mg once daily compared with placebo.

$H_a$ : There is a difference in the change from baseline in pre-dose FEV1 at week 12 post-baseline for the patients treated with QAW039 150 mg once daily compared with placebo.

##### Familywise type I error rate control

The familywise type I error rate will be controlled at the two-sided 5% level across the primary and secondary null hypotheses using the closed testing procedure shown in [Figure 9-1](#) using the graphical method of [Bretz et al 2009](#). In this closed testing procedure, the primary null hypothesis about pre-dose FEV1 acts as a gatekeeper for the secondary null hypotheses.

**Figure 9-1 Closed testing procedure for primary and secondary objectives**

Vertices with associated weights denote the individual null hypotheses and their local significance levels. Directed edges between the vertices specify how the local significance levels are propagated in case of significant results.  $\epsilon$  is set to a very small number in practice. Abbreviations: FEV1 (forced expiratory volume in 1 second); AQLQ+12 (asthma quality of life questionnaire for 12 years and older).

Initially, the alpha is assigned to the primary null hypothesis. Once the primary null hypothesis has been rejected, then 98% of the alpha will be distributed equally amongst the secondary null hypotheses of daytime asthma symptoms and total daily SABA use, respectively, and 2% of the alpha will be assigned to the null hypothesis for AQLQ+12. If one of the secondary null hypotheses is rejected, its local significance level will be propagated to the other secondary null hypotheses as illustrated in Figure 9-1.

### Statistical model for primary variable

The primary efficacy variable will be analyzed on FAS using an analysis of covariance (ANCOVA) model with factors for treatment group, age group (<18 vs.  $\geq 18$  years), use or non-use of a second asthma controller medication at study entry, and region, as well as the baseline daytime asthma symptom score, baseline total daily SABA use and baseline pre-dose FEV1 as continuous linear covariates.

The least squares mean (“adjusted mean”) change from baseline for each treatment group, the difference in the least squares mean changes between the two treatment groups (QAW039 150mg – placebo), and the two-sided adjusted 95% confidence interval along with the p-value for the difference will be obtained and combined from the primary analysis model through the multiple imputation approach described in Section 9.4.3. The superiority of QAW039 150 mg once daily to placebo as add on to SoC asthma therapy is established if the two-sided p-value is less than 0.05 and the 95% confidence intervals lie entirely to the right of 0 L.

### Summary statistics for the primary variable

Summaries of absolute values and change from baseline in pre-dose FEV1 by treatment group and visit will be presented. Figures will be produced to visually show the mean pre-dose

FEV1 and the mean change from baseline in pre-dose FEV1 by visit over study period for each treatment group.

### 9.4.3 Handling of missing values/censoring/discontinuations

Despite all attempts to ensure complete follow-up for all patients, some patients may not be followed for pre-dose FEV1 for the whole planned study duration. Missing data after discontinuation of double-blind study treatment will be imputed using the jump to reference approach (Carpenter et al 2013). Intermittent missing data prior to discontinuation of double-blind study treatment will be imputed under a missing at random assumption.

A large number of imputed datasets will be created, with their number chosen based on computational feasibility, but at least 1,000. Each dataset will be analyzed using the model described in Section 9.4.2 and the results will be combined using Rubin's rule (Barnard and Rubin 1999) for final inference.

The average of the two FEV1 assessments will only be formed after multiple imputations so that if one of the two FEV1 assessments at a visit is missing, the average will be between the one available assessment and a second imputed assessment. In the situation when both FEV1 values at the randomization visit are missing, the values from preceding visits will be used as described in Section 9.4.1. Retrieved data after the discontinuation of study drug (retrieved drop-out) will remain in the analysis without further imputation for all treatment groups.

